6.3 Clinical Study Duration

Enrollment is anticipated to take approximately twelve (12) months. Post-procedure assessments will occur at 3-, 6-, and 12-months. The total study duration is anticipated to be approximately twenty-four (24) months.

6.4 Clinical Study Sample Size and Clinical Sites

Up to one hundred (100) patients will be treated at up to fifteen (15) clinical sites in Europe. The sample size will include only those that complete an ablation procedure using the AcQMap technology (Treatment Subjects).

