1 CLINICAL STUDY SYNOPSIS

STUDY TITLE	Utilizing Novel Dipole Density Capabilities to Objectively Visualize the Etiology of Recurrent Atrial Fibrillation Following a Failed AF Ablation (RECOVER AF)
DEVICE NAME	AcQMap® High Resolution Imaging and Mapping System
DEVICE SHORT NAME	AcQMap
DEVICE COMPONENTS	
The AcQMap System consists of the following components:
 
• The AcQMap 3D Imaging and Mapping Catheter (AcQMap Catheter)• The AcQGuide® Steerable Delivery Sheath• The AcQMap Console• The AcQMap Workstation• The AcQMap Patient Electrode Kit
INDICATION FOR USE (INTENDED USE)	The AcQMap Imaging and Mapping System is intended to be used in the right and/or left atria to visualize the selected chamber and display atrial electrical impulses.
SPONSOR	Acutus Medical®, Inc. [name] [name]
STUDY OBJECTIVES	To evaluate the performance and efficiency of the AcQMap Imaging and Mapping System in an ablation retreatment procedure for recurrent atrial fibrillation following a failed AF ablation
STUDY DESIGN	A prospective, single-arm, multi-center, multi-national, non-randomized, post-market study designed to provide clinical data regarding the use of the AcQMap High Resolution Imaging and Mapping System during an atrial fibrillation retreatment ablation procedure. The patient population includes men and women, eighteen (18) years of age or older, who in the past twenty-four (24) months have had no more than two (2) previous left-atrial ablations for AF treatment. The treatment plan must include evaluation and ablation (as indicated) of pulmonary vein reconnections plus AcQMap guided non-PV substrate ablation. Subject assessments will occur at screening, procedure, hospital discharge, 3-, 6-, and 12-months.
SAMPLE SIZE	Enrollment of up to one hundred (100) subjects that complete the ablation procedure using the AcQMap System
CLINICAL SITES	Up to fifteen (15) Clinical Sites
DURATION	Enrollment is anticipated to take approximately twelve (12) months. Post-procedure assessments will occur at 3-, 6-, and 12-months. The

	
total study duration is anticipated to be approximately twenty-four (24) months.

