5.2 Clinical Study Design Justification

Previous clinical studies utilizing the AcQMap System in an ablation procedure for supraventricular tachycardias (SVTs) have initially demonstrated an acceptable safety profile when mapping and imaging cardiac chambers. The RECOVER AF study is a prospective, single-arm, multi-center, multi-national, non-randomized, post-market study designed to provide clinical data regarding the use of the AcQMap High Resolution Imaging and Mapping System during an atrial fibrillation retreatment ablation procedure. Recording of all Serious Adverse Events/Device Effects occurring during the first twenty-four (24) hours post-procedure will be used to assess the safety related to the AcQMap Catheter, AcQGuide Steerable Sheath, and the AcQMap System.

Since it is hypothesized the technology advances of dipole density mapping may better identify and more precisely direct lesion locations during atrial arrhythmia ablations, the study is additionally designed to record longer term (6- and 12-month) data on the effectiveness of the ablation procedure in the treatment of the arrhythmia. An analysis of treatment success (defined as freedom from atrial arrhythmias at 6- and 12-months), compared to literature based historical controls, may offer insight regarding the ability of the AcQMap System to effectively and accurately identify appropriate ablation targets.

Automatic, instantaneous, and simultaneous 3D display of the LA surface with associated charge densities may potentially shorten atrial arrhythmia ablation procedure time and provide an intuitive tool to rapidly identify and guide effective treatment.

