6.2.1 Measurable Objective

The measurable objectives are a descriptive analysis of the following:

- At the procedure conclusion, confirmation of electrical isolation of all pulmonary veins and elimination/modification of all non-PV targets as identified by the AcQMap System

- Recording of all subjects who are atrial fibrillation free from events lasting > 30 seconds at 6- and 12-months as measured by a 48-hour continuous ECG
 - A subset analysis of AAD use
 - A subset analysis of subjects with freedom from AF/AT/AFL events lasting > 30 seconds as measured by a 48-hour continuous ECG
- Documentation of procedure data including total time, fluoroscopy time, ablation times for PVI, and ablation times for non-PV targets
- Safety - Recording of all device and procedure related safety events through twenty-four (24) hours post-ablation

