6.5 Clinical Study Enrollment Definitions

For the purposes of this clinical study, the following definitions regarding the status of a subject will apply:

Pre-Treatment Subject – Any subject who has signed an informed consent form, is deemed study eligible by meeting all of the inclusion and none of the exclusion criteria, and who has the venous access portion of the ablation procedure initiated. Pre-Treatment subjects that do not complete the AcQMap procedure will be followed for adverse events through hospital discharge. In addition to the discharge eCRF, a study completion eCRF will be completed. No follow-up beyond the hospital discharge will be required.

Treatment Subject – Any pre-treatment subject who completes the ablation procedure using the AcQMap System. A completed ablation procedure is defined as a procedure where the PVI was evaluated and additional non-PV targets were mapped and ablated using the AcQMap System. Treatment subjects should be followed for all study outcome measures for the full duration of the clinical study.

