8 STATISTICAL METHODS

Analysis of all data generated by the clinical study will be reported with descriptive statistics. There are no hypotheses established for the study therefore, the study sample size has not been established for power.

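### The acute success rate is implicitly based on completed AcQMap procedures only, and the plan adds no all-attempted rate and no table of non-completions

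*Combined protocol and SAP*

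**What the plan says.** The objective in section 6.1 is to evaluate the performance and efficiency of the mapping system in repeat AF ablation. The acute outcome in section 6.2.1 is isolation of all pulmonary veins together with "elimination/modification of all non-PV targets as identified by the AcQMap System". No denominator is attached to it, there or in the synopsis.

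The synopsis gives the sample size as "Enrollment of up to one hundred (100) subjects that complete the ablation procedure using the AcQMap System", and section 6.4 repeats the restriction: "The sample size will include only those that complete an ablation procedure using the AcQMap technology (Treatment Subjects". Section 6.5 defines a completed procedure as "a procedure where the PVI was evaluated and additional non-PV targets were mapped and ablated using the AcQMap System".

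Section 6.5 also defines a wider group, Pre-Treatment Subjects: consented, eligible, and with venous access begun. For those who do not go on to complete, adverse events are collected until discharge, a discharge eCRF and a study completion eCRF are filled in, and "No follow-up beyond the hospital discharge will be required". By contrast, "Treatment subjects should be followed for all study outcome measures for the full duration of the clinical study".

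Section 8 has two sentences. One is "Analysis of all data generated by the clinical study will be reported with descriptive statistics"; the other says that there are no hypotheses and that the sample size was not set for power. No analysis set is named.

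**The concern.** Entry to the counted set depends partly on what the study evaluates. A subject whose mapping fails, whose procedure is abandoned, or whose mapped target is not ablated never becomes a Treatment Subject. Neither does a subject in whom the map shows no non-PV target. None of them uses up a place among the 100, so recruitment can continue until enough completers have been obtained.

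If the acute rate is then reported on completers alone, one route to failure has been removed before counting starts. The same applies to efficiency: long or abandoned attempts may be missing from procedure and fluoroscopy times. Section 13.2 foresees use of the results in a regulatory filing and a multi-centre publication, where readers may take the rate as applying to every patient in whom the system was tried. No test or error rate is at stake; what is at stake is the meaning of the reported percentages.

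**Working it through.** **Step 1: which denominator do the documents imply?**

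- Sections 6.4 and 6.5 point to Treatment Subjects: they are the counted sample and the group followed for every outcome.
- Section 8 and the synopsis promise description of all data, which could include everyone with venous access begun.
- Section 11.3 keeps screened but non-enrolled subjects out of outcome analyses. Whether that covers non-completers depends on what enrolled means. The synopsis applies the word to completers; section 6.5 treats both groups under its enrolment definitions.

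Completers are therefore the natural reading, though not a stated rule.

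**Step 2: could non-completions be counted?** Yes, from the two eCRFs that section 6.5 requires for each non-completer. The identification numbers of section 11.2 would not do, because they are issued at consent and so include people who never reach venous access. Malfunction reports (9.4), device-deficiency monitoring (11.11) and deviation records (11.13) may hold some of the reasons. No section plans to tabulate or score them.

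**Step 3: the planned sample size.** The 100 is a cap with no alpha, power or expected rate behind it, so there is nothing to reproduce.

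**Step 4: illustration of size.** Only the 100 completers come from the documents. The success rate and the number of non-completers, k, are assumptions. With 95 acute successes among 100 completers:

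- all non-completers failures: 95/(100 + k)
- all non-completers successes: (95 + k)/(100 + k)

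| k | All failures | All successes |
|---|---|---|
| 0 | 95/100 = 95.0% | 95/100 = 95.0% |
| 2 | 95/102 = 93.1% | 97/102 = 95.1% |
| 10 | 95/110 = 86.4% | 105/110 = 95.5% |
| 20 | 95/120 = 79.2% | 115/120 = 95.8% |

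**Step 5: direction.** Let m non-completers be failures and n be subjects with a completed map, no target and isolated veins, counted as successes. With completer success p, the completer rate overstates the all-attempted rate when (100p + n)/(100 + m + n) < p, that is, when n < m × p/(1 − p). At p = 0.95 this is n < 19m. Check with m = 1: n = 19 gives 114/120 = 95.0% (equal), and n = 20 gives 115/121 = 95.04% (no overstatement). At p = 0.90 and 0.80 the limits are 9m and 4m.

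**Step 6: the proposed scoring, worked through.** Assume 10 non-completers: 2 stopped for reasons unrelated to the system, 4 system-related failures, and 4 with a completed map, no target and isolated veins.

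- All-attempted: (95 + 4)/110 = 90.0%
- Leaving out the 2 unrelated stops: 99/108 = 91.7%
- Per-procedure: 95/100 = 95.0%

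**Step 7: 12-month AF freedom.** Assume 60/100 among completers with complete follow-up, and 10 non-completers with unknown rhythm. The bounds over all attempts are 60/110 = 54.5% and 70/110 = 63.6%.

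**The case against.** The strongest reply is that the restriction is deliberate. The synopsis says the treatment plan has to include assessment of the pulmonary veins plus AcQMap-guided non-PV ablation, and the definition of completion mirrors this. A per-procedure set is a reasonable choice for a descriptive post-market study of that strategy, and leaving out a subject with no target is not the same as leaving out a mapping failure. This stands: the set itself is not an error. It does not answer the absence of any companion figure showing how often the strategy could not be delivered.

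It can also be said that all data are to be described and that existing records hold the reasons. That makes the remedy cheap, but it neither names a denominator nor plans a table.

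Four stronger readings are tempting and are not supported:

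- A reader might infer that the acute rate must be inflated. Step 5 shows that the direction depends on the mix of non-completers, and the effect is zero if every attempt qualifies.
- A reader might infer that the denominator is wholly open. Sections 6.4 and 6.5 imply completers.
- A reader might infer that failed attempts are lost to safety reporting. They are observed for adverse events until discharge.
- A reader might infer that the longer-term results, which section 5.2 says may be "compared to literature based historical controls", are biased in a known direction. That depends on the denominators used in literature that the documents do not describe.

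**Conclusion.** The point holds as a reporting gap that should be closed. Treatment Subjects are a valid per-procedure set. Used alone, they yield an acute rate that can omit failures of the system being evaluated, with replacement permitted by the way the cap is counted and with no planned display of how many attempts were omitted or why. The size cannot be derived from the documents. Under the assumed 95% completer success, 10 non-completers would put the all-attempted rate anywhere from 86.4% to 95.5%, and 20 would put it from 79.2% to 95.8%; with none, nothing changes. A completer who does not meet the acute outcome still counts as a failure, so the selection removes some failures and not all of them. The 6- and 12-month results describe Treatment Subjects only and should be labelled as such.

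**What to change.** Amend sections 6.4, 6.5 and 8, with the synopsis to match:

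1. Report the acute outcome side by side for all Pre-Treatment Subjects (venous access begun, Treatment Subjects included) and for Treatment Subjects.
2. Tabulate every Pre-Treatment Subject who did not complete, by reason, from the discharge and study completion eCRFs already required. Add a reason field if those forms lack one. Keep system-related causes (catheter, sheath, console, workstation, mapping failure, change of system) separate from unrelated stops, both before and after catheter deployment. Allow a complication to be recorded together with a mapping failure.
3. In the all-attempted rate, count non-completers as not successful. The one exception is a subject with a completed map and no identified target, who is assessed on PV isolation. Add one sensitivity rate that leaves out only stops unrelated to the system.
4. Report procedure and fluoroscopy times for all attempts where recorded, and for completers.
5. State that 6- and 12-month AF freedom applies to Treatment Subjects, and give the number of attempted subjects not followed. Bounds over all attempts, as in step 7, are optional.

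Cost: the procedure eCRF has to be completed as far as possible for non-completers, PV isolation status included. Section 7.2.2 does not limit procedure data to completers, but section 6.5 names only the other two forms for non-completers. A protocol amendment is needed under section 11.15.1. The reported rates may be less favourable. No subject's treatment or visits change.

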6.5 Clinical Study Enrollment Definitions

For the purposes of this clinical study, the following definitions regarding the status of a subject will apply:

Pre-Treatment Subject – Any subject who has signed an informed consent form, is deemed study eligible by meeting all of the inclusion and none of the exclusion criteria, and who has the venous access portion of the ablation procedure initiated. Pre-Treatment subjects that do not complete the AcQMap procedure will be followed for adverse events through hospital discharge. In addition to the discharge eCRF, a study completion eCRF will be completed. No follow-up beyond the hospital discharge will be required.

Treatment Subject – Any pre-treatment subject who completes the ablation procedure using the AcQMap System. A completed ablation procedure is defined as a procedure where the PVI was evaluated and additional non-PV targets were mapped and ablated using the AcQMap System. Treatment subjects should be followed for all study outcome measures for the full duration of the clinical study.

6.6 Clinical Study Population

The patient population will consist of men and women eighteen (18) years of age or older, scheduled for a repeat endocardial ablation of AF following a failed ablation for atrial fibrillation.

A potential study subject will be eligible for study enrollment only if all the following inclusion and none of the exclusion criteria apply:

6.6.1 Inclusion Criteria

- IC 1 Male or female eighteen (18) years of age or older
- IC 2 Currently scheduled for a repeat endocardial ablation of AF
- IC 3 Willingness, ability, and commitment to participate in baseline and follow-up evaluations for the full length of the study
- IC 4 Willing and able to give informed consent

6.6.2 Exclusion Criteria

- EC 1 In the opinion of the Investigator, any known contraindications to a left-atrial ablation or concerns for left-atrial thrombus
- EC 2 No more than two previous left-atrial ablations
- EC 3 Atrial fibrillation secondary to electrolyte imbalance, thyroid disease, or any other reversible or non-cardiac cause
- EC 4 Structural heart disease or implanted devices as described below:
 - a. An implanted pacemaker or ICD
 - b. Previous cardiac surgery, ventriculotomy, or atriotomy (excluding atriotomy for CABG)
 - c. Previous cardiac valvular surgical or percutaneous procedure, or prosthetic valve
 - d. Interatrial baffle, closure device, patch, or PFO occluder
 - e. Presence of a left atrial appendage occlusion device
 - f. Unstable angina or ongoing myocardial ischemia
- EC 5 History of blood clotting or bleeding disease
- EC 6 Pregnant or lactating (current or anticipated during study follow up)
- EC 7 Current enrollment in any study protocol sponsored by Acutus Medical or any other study that may impact the results of RECOVER AF
- EC 8 Any other condition that, in the judgment of the investigator, makes the patient a poor candidate for this procedure, the study,

or compliance with the protocol (includes vulnerable patient population, mental illness, addictive disease, terminal illness with a life expectancy of less than two years, extensive travel away from the research center, etc.)

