OUTCOME MEASURES	
The measurable objectives are a descriptive analysis of the following:
 
 • At the procedure conclusion, confirmation of electrical isolation of all pulmonary veins and elimination/modification of all non-PV targets as identified by the AcQMap System • Recording of all subjects who are atrial fibrillation free from events lasting > 30 seconds at 6-, and 12-months as measured by a 48-hour continuous ECG 
 ○ A subset analysis of AAD use ○ A subset analysis of subjects with freedom from AF/AT/AFL events lasting > 30 seconds as measured by a 48-hour continuous ECG • Documentation of procedure data including total time, fluoroscopy time, ablation times for PVI, and ablation times for non-PV targets • Safety – Recording of all device and procedure related safety events through 24 hours post-ablation
INCLUSION CRITERIA	
The patient population will consist of men and women eighteen (18) years of age or older, scheduled for a repeat endocardial ablation of AF following a failed ablation for atrial fibrillation.
 
A potential subject will be eligible for study enrollment only if all the following inclusion and none of the exclusion criteria apply:
 
IC 1 Male or female eighteen (18) years of age or older IC 2 Currently scheduled for a repeat endocardial ablation of AF IC 3 Willingness, ability, and commitment to participate in baseline and follow-up evaluations for the full length of the study IC 4 Willingness and ability to give informed consent

EXCLUSION CRITERIA	
EC 1 In the opinion of the Investigator, any known contraindication to a left-atrial ablation or concerns for left-atrial thrombus EC 2 No more than two (2) previous left-atrial ablations EC 3 Atrial arrhythmias secondary to electrolyte imbalance, thyroid disease, or any other reversible or non-cardiac cause EC 4 Structural heart disease or implanted devices as described below:
 
 a. An implanted pacemaker or ICD b. Previous cardiac surgery, ventriculotomy, or atriotomy (excluding atriotomy for CABG) c. Previous cardiac valvular surgical or percutaneous procedure, or prosthetic valve d. Interatrial baffle, closure device, patch, or PFO occluder e. Presence of a left atrial appendage occlusion device f. Unstable angina or ongoing myocardial ischemia

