6.2 Clinical Study Design

The clinical study is a prospective, single-arm, multi-center, multi-national, non-randomized, post-market study designed to provide clinical data regarding the use of the AcQMap High Resolution Imaging and Mapping System during an AF retreatment ablation procedure. The patient population includes men and women, eighteen (18) years of age or older, who in the past twenty-four (24) months have had no more than two (2) previous LA ablations for AF treatment. Subject assessments will occur at screening, procedure, hospital discharge, 3-, 6-, and 12-months.

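### Exclusion criterion EC 2 is written the wrong way round and, read literally, bars patients with one or two prior left-atrial ablations

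*Combined protocol and SAP*

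**What the plan says.** The eligibility rule is in Section 6.6: a patient may enter "only if all the following inclusion and none of the exclusion criteria apply". Section 6.5 builds the same rule into the definition of a Pre-Treatment Subject, who "is deemed study eligible by meeting all of the inclusion and none of the exclusion criteria". Treatment Subjects are drawn from that group, and under Section 6.4 they make up the sample of up to 100.

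The second item in the exclusion list of Section 6.6.2 is "EC 2 No more than two previous left-atrial ablations". The synopsis has the same item: "EC 2 No more than two (2) previous left-atrial ablations".

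The intended population is described in two other places. Section 6.2 says the study is for adults "who in the past twenty-four (24) months have had no more than two (2) previous LA ablations for AF treatment". The study design row of the synopsis likewise describes patients who "have had no more than two (2) previous left-atrial ablations for AF treatment", with the same 24-month window.

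No inclusion criterion states a number of prior ablations or a time window. The nearest is "IC 2 Currently scheduled for a repeat endocardial ablation of AF", which implies at least one earlier AF ablation.

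**The concern.** A condition that qualifies a patient in Section 6.2 disqualifies the same patient in Section 6.6.2. Because the exclusion list is the operative text for screening, the contradiction has practical consequences. Section 11.13 treats any departure from the protocol as a deviation and expects waivers of exclusion criteria to be rare. Section 11.11 lists review of how subjects were screened and selected among the monitoring activities. A monitor applying EC 2 as printed would have to query every subject with one or two prior ablations.

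The second difficulty is the counting rule. Section 6.2 counts ablations done for AF in the last 24 months. EC 2 counts left-atrial ablations with no time limit and no stated indication. A site can guess the intended direction of EC 2 from the design section. It cannot guess which counting rule was meant, because both are plausible, so up to fifteen sites could screen differently. This also affects interpretation: Section 5.2 contemplates comparing treatment success with historical controls from the literature, which requires knowing exactly who was eligible. If the number of prior ablations is related to recurrence, differing site practice would also shift case mix. That relation is plausible, but the documents give no data on it.

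**Working it through.** The check is logical; the plan gives no figure to reproduce on this point.

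**Notation.** Let L be the lifetime number of prior left-atrial ablations and R the number of those done for AF in the past 24 months, so R ≤ L.

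**Inputs.**
- Section 6.6: a patient is eligible only if every exclusion condition is false.
- EC 2 (Section 6.6.2 and synopsis): the exclusion condition is true when L ≤ 2.
- Section 6.2 and synopsis design: the population has R ≤ 2.
- IC 2: the procedure is a repeat AF ablation. I take the earlier one to have been left-atrial, so L ≥ 1. A patient with L = 0 would in any case also be barred by EC 2 as written.

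**Step 1: EC 2 as written.** A patient passes only if L ≤ 2 is false, that is, if L ≥ 3.

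**Step 2: comparison of the rules.**

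| Prior ablations | Section 6.2 | EC 2 as written | EC 2 reversed, lifetime count | EC 2 reversed, AF ablations in past 24 months |
|---|---|---|---|---|
| L = 1 | in | **out** | in | in |
| L = 2 | in | **out** | in | in |
| L ≥ 3, R ≤ 2 | in | in | **out** | in |
| L ≥ 3, R ≥ 3 | out | **in** | out | out |

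Bold marks disagreement with Section 6.2.

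**Step 3: size.** Among patients with L = 1 or 2, the share passing EC 2 as written is 0%. If f is the fraction of enrolled subjects with L ≥ 3, the number of literal eligibility violations among 100 Treatment Subjects is 100 × (1 − f). The documents do not give f. With f = 0 the result is 100 × (1 − 0) = 100, which is the upper bound.

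**Step 4: patients who satisfy both texts.** The only group eligible under both Section 6.2 and EC 2 as written is L ≥ 3 with R ≤ 2. If the sponsor meant a lifetime limit of two, that group falls outside the intended population and the overlap is empty.

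**Step 5: after reversing the direction only.** The first two rows agree with Section 6.2 under either count. The third row does not: a patient with three lifetime ablations, two of them in the last 24 months, is in under Section 6.2 and out under a lifetime EC 2. The missing AF qualifier has a similar effect. A patient with two left-atrial ablations for AF and one for another arrhythmia has a count of two under Section 6.2 and three under EC 2.

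**The case against.** The strongest reply is that this is an evident drafting slip. The phrase in EC 2 is the one used to define the population in Section 6.2, so it looks like an inclusion phrase placed in the wrong list. Nothing suggests that any site would seek out only patients with three or more ablations. On this view the realistic harm is an ambiguous screening rule and disputed deviation records. That is fair as a description of likely behaviour, and it is why the figure of 100 is only an upper bound. It does not cure the text, because the list as printed decides who is eligible and what counts as a deviation.

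A second point also stands: the conflict is total only for patients with one or two lifetime ablations. Under the 24-month wording, some patients with three or more satisfy both texts, so the 0% figure belongs to the one-or-two group and not to everyone Section 6.2 could admit.

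Third, the study is single-arm and descriptive, and Section 8 states that it has no hypotheses and was not sized for power. No error rate or sample size is affected, and an effect on case mix is an assumption. This limits the statistical consequence but leaves the eligibility contradiction untouched.

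Finally, the two defects differ in weight. The reversed direction is a plain error, and the counting-rule mismatch is secondary. They concern the same criterion and are best settled together.

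**Conclusion.** The concern holds. EC 2 as written, in both places, excludes every patient with one or two prior left-atrial ablations, although the design statements place those patients in the study population. The text is complete and current, and no other section corrects it. Under literal application up to 100 of 100 Treatment Subjects would be eligibility violations; the true number depends on how many have three or more lifetime procedures, which the documents do not say. Reversing the direction removes the main conflict but leaves the 24-month window and the AF qualifier unreconciled. The conclusion rests on the wording of the eligibility rule and on IC 2 implying at least one prior left-atrial ablation. It does not depend on any link between prior-ablation count and outcome. Because this is the operative eligibility rule, it must be corrected.

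**What to change.** Reword EC 2 in the synopsis and in Section 6.6.2 so that it excludes patients with *more than* two prior left-atrial ablations, matching the population already described in Section 6.2 and the synopsis design row. In the same amendment, the sponsor should decide whether the limit applies to the past 24 months or to the patient's lifetime, and whether it covers only ablations for AF. The same rule should then appear in all four places: synopsis design, synopsis EC 2, Section 6.2 and Section 6.6.2. The eligibility check on the eCRF should carry it too. If any subjects have already been screened, their prior-ablation counts should be checked against the corrected rule.

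The cost is small. The text edits are short, and Section 7.2 already collects the dates of previous AF ablations, so either window can be verified for those procedures. If ablations for other arrhythmias are to count, the medical history must capture them as well. Under Section 11.15.1 the amendment needs written ethics committee acknowledgement or approval before it takes effect. Reversing the direction does not change the intended enrolment. The choice of window does decide whether patients with three or more lifetime ablations, at most two of them recent, may enter.
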